5.4.3. NA Treatment Completion Criteria

5.4.3.1. NA Treatment Completion Criteria During The Study

The count and proportion of participants who met the NA treatment completion criteria (as defined in Section 5.2.1) at any time during the study, regardless of the treatment duration, will be summarized by intervention arm.

Starting at Week 44, the incidence of participants who did not meet the NA treatment completion criteria will be summarized by intervention arm at each timepoint during the study, accompanied by the distribution of each of the 4 criteria that is not met. The NA treatment completion criteria are based on a threshold for the laboratory tests of ALT, HBV DNA, HBeAg and HBsAg as defined in Section 5.2.1.

5.4.3.2. NA Treatment Completion Criteria During FU

The count and proportion of participants who met the NA treatment completion criteria (as defined in Section 5.2.1) at any time during the FU phase, regardless of the treatment duration, will be summarized by intervention arm. All of NA treatment completion criteria will be checked based on clinical laboratory tests in FU phase.

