JNJ-3989 was generally safe and well tolerated with no deaths, serious adverse events (SAEs) considered at least possibly related to the study intervention, or adverse events (AEs) leading to study intervention discontinuation. All AEs were mild to moderate, with exception of 1 severe blood creatine phosphokinase increased in 1 CHB participant. All reported injection site reactions (ISRs) were mild. Adverse events and laboratory abnormalities were distributed across all dose levels and also occurred on placebo treatment, except for mild ISRs, which were only reported in participants on JNJ-3989 treatment. Most reported laboratory abnormalities were isolated incidences and resolved while on study treatment.

Efficacy was assessed using snapshot data through 02 May 2019. Antiviral activity data were available for 56 CHB participants who received 3 subcutaneous injections of 25 to 400 mg JNJ-3989 every 4 weeks. The antiviral activity data showed that administration of JNJ-3989 at doses of 25 to 400 mg resulted, on average, in pronounced HBsAg decline which was generally sustained at least until Day 168 (ie, 16 weeks after last dose) across all doses. No apparent dose response was observed at doses between 100 and 400 mg JNJ-3989; a reduced mean decline was observed at the lower dose of 25 mg. Data on the 50 mg dose were still emerging at the time of protocol writing. Treatment status (ie, virologically suppressed or not treated) did not seem to affect HBsAg changes. Other measurable serological and virological markers (HBV DNA, HBV RNA, HBeAg, hepatitis B core-related antigen [HBcrAg]) also showed responses to JNJ-3989, indicating that JNJ-3989 shows target activity on all detectable viral products.

JNJ-6379

At the time of protocol writing, 98 adult healthy and 41 CHB participants have been dosed with JNJ-6379 in 4 completed Phase 1 studies (56136379HPB1001, 56136379HPB1002, 56136379HPB1003, and 56136379HPB1004). Another Phase 1 study in healthy participants is also completed and clinical study report writing is currently ongoing (56136379HPB1005). In addition, data are available from 148 participants in the ongoing Phase 2a study, 56136379HPB2001, also referred to as Jade.

Human Pharmacokinetics and Product Metabolism

Single Dose Studies in Healthy Participants

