6.6. Individual Participant NA Treatment Completion Criteria

After a fixed duration of 48 weeks, participants will complete treatment with JNJ-3989 and/or JNJ-6379. If all of the following criteria are met based on clinical laboratory tests performed at Week 44, treatment with NA will also be completed at Week 48 (ie, the next scheduled visit after Week 44):

- The participant has ALT <3x ULN, AND
- The participant has HBV DNA <LLOQ, AND
- The participant is HBeAg-negative, AND
- The participant has HBsAg <10 IU/mL.

Note: In case of ALT elevation $\ge 3x$ ULN at Week 44 the investigator must consider different potential causes of increased ALT to ensure appropriate work up and management as needed. If the ALT elevation is unrelated to HBV activity and/or <3x ULN by treatment Week 48, NA completion may be considered at the discretion of the investigator and in consultation with the sponsor.

Participants who do not meet the above criteria at Week 48 should continue NA treatment during the 48-week follow-up. If the above criteria are met during the follow-up phase based on clinical laboratory tests performed at or before Follow-up Week 42 (Follow-up Week 36 for Arm 6), NA treatment should be stopped at or before Follow-up Week 48 (ie, the next scheduled visit after the laboratory test was performed) and the follow-up schedule should be extended to 48 weeks after the end of NA treatment. If NA treatment completion criteria are not met based on clinical laboratory tests performed at or before Follow-up Week 42 (Follow-up Week 36 for Arm 6), the follow-up phase will not be extended, but the participant will continue NA treatment and complete the study at Follow-up Week 48.

The investigator should consider to re-start NA treatment per local standard of care at the EOS visit ([Extended] Follow-up Week 48) for participants who met the NA treatment completion criteria at Week 48 or during the follow-up phase, who did not re-start NA treatment during the follow-up phase, and who did not achieve and maintain HBsAg seroclearance. NA will not be provided by the sponsor after the final study visit.

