2.1. Analysis Phases and Visit Windows

2.1.1. Analysis Phase

The analysis phases are defined in [Table 1](#) below.

Table 1: Analysis Phases Start and End Dates

Analysis phase	Start date	End date
Screening	The date of signing the informed consent	1 day before the first study agent intake
Double-blind Study intervention	Date of first study agent intake	The maximum of last intake of JNJ-3989/placebo, last intake of JNJ-6379/placebo and Week 48 date + 5 days or cut-off date*, whichever comes first
Follow-up	End of the double-blind study intervention phase + 1 day	If the participant stops NA treatment at/up to Week 48, study termination date (date of last contact) or cut-off date*, whichever comes first
		If the participant completes NA treatment post Week 48 during the follow-up phase, (date of the last NA intake + 5 days) or cut-off date*, whichever comes first
		If the participant never completes NA treatment during follow-up phase, trial termination date (date of last contact) or cut-off date*, whichever comes first
Extended Follow-up #	End of the follow-up phase + 1 day	Trial termination date (date of last contact) or cut-off date*, whichever comes first

Note: +5 days is only attributed to adverse events and concomitant medications.

*Cutoff dates will be defined to match the prespecified timepoints for IDMC safety monitoring, interim analysis and the primary analysis, respectively.

The extended follow-up phase is only for the participants who completed the NA treatment during the follow-up phase

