5. EFFICACY

All efficacy data will be analyzed by intervention arm, analysis phase and over time (when applicable). The primary analysis set will be the mITT analysis set (see definition in Section 2.3). Selected efficacy endpoints will be also analyzed using the ITT, and PP analysis sets, respectively (see definition in Section 2.3). Efficacy assessments over time will be performed at the analysis time points defined in Section 2.1.

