5.4.4. NA Re-Treatment During Follow-Up

The number and proportion of participants who meet the criteria for NA re-treatment at any time during FU will be summarized descriptively by intervention arm. Only the subset of participants who meet the NA treatment completion criteria at any time during the study and actually stop NA treatment will be included in the analysis.

The proportion of participants who actually re-started NA treatment during the follow-up phase on the basis of the 'Study Drug Administration for ETV, TDF or TAF' CRF page will be summarized separately over time (e.g. FU Week12, 24, 48, etc.) by intervention arm.

Due to the Protocol Amendment #4 to update the criteria for NA re-treatment for participants who discontinued NA treatment at Week 48, the participants who met NA re-treatment criteria in follow-up will also be listed along with their respective criterion. The proportion of participants who met the criteria according to the flag on the CRF page of 'NA Re-treatment Criteria Assessment' during the follow-up phase was summarized over time by intervention arm prior to Protocol Amendment 4 approval.

A cross-tabulation of participants who actually re-started NA treatment (re-started/not restarted) versus participants who met the above criteria (met/not met) will be presented over time.

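### SAP 5.4.3.2 does not exclude participants who already completed NA at Week 48, so the follow-up completion endpoint mixes persistence of the Week 44 response with first-time completion

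*SAP*

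**What the plan says.** SAP 5.4.3.2 counts participants who met the four laboratory criteria of SAP 5.2.1 "at any time during the FU phase, regardless of the treatment duration, will be summarized by intervention arm". It adds: "All of NA treatment completion criteria will be checked based on clinical laboratory tests in FU phase". It names no subset and no denominator, so the general rule of SAP 5 applies: "The primary analysis set will be the mITT analysis set".

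SAP Table 1 (section 2.1.1) gives Week 48 completers a follow-up phase of their own. Its end date is set as follows: "If the participant stops NA treatment at/up to Week 48, study termination date (date of last contact"), or the cut-off date if that comes first. Their off-NA laboratory values therefore fall inside the window that 5.4.3.2 searches. Late completers are a separate row ("If the participant completes NA treatment post Week 48 during the follow-up phase"), and their follow-up phase ends 5 days after the last NA intake.

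Protocol 6.6 raises completion in follow-up for one group only: "Participants who do not meet the above criteria at Week 48 should continue NA treatment during the 48-week follow-up". If they then qualify on a test at or before Follow-up Week 42 (Week 36 for Arm 6), NA is to be stopped. The note to the protocol schema is worded for the same group.

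The next SAP section, 5.4.4, states its population: "Only the subset of participants who meet the NA treatment completion criteria at any time during the study and actually stop NA treatment". Section 5.4.3.2 has no such sentence.

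Protocol 9.4.1.3 plans a stratified CMH comparison of arms, with 90% CIs, for this endpoint.

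**The concern.** A participant who stopped NA at Week 48 has no NA left to complete. Follow-up completion is informative only as a measure of how many further participants qualify after the 48-week course. SAP 5.4.3.1 already reports meeting the criteria at any time during the study, so 5.4.3.2 adds something only if it isolates the late qualifiers.

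Repeat counting is plausible. A Week 48 completer has 14 scheduled follow-up visits, starting at Follow-up Week 2, and needs to qualify at only one of them. Protocol 2.2.1 reports that three doses of JNJ-3989 "resulted, on average, in pronounced HBsAg decline which was generally sustained at least until Day 168 (ie, 16 weeks after last dose) across all doses".

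At stake is the between-arm reading. Arms with more Week 48 responders carry more of them into the follow-up count, so a difference labelled as occurring during follow-up can partly or wholly repeat the primary comparison.

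**Working it through.** The documents give no figure for this endpoint, so there is nothing to reproduce. The check is how far the literal count can depart from a count of first-time completers.

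**Inputs**
- p, the Week 48 response rate: 25% in a JNJ-3989 arm of 90 (the lower end of the 25–35% planning range in Protocol 9.2), and 5% in control Arm 6 of 45 (Protocol 9.2).
- q, the share of Week 48 responders who meet all four criteria at one or more follow-up visits: not in the documents; assumed 0.5 to 1.0.
- r, the share of Week 48 non-responders who first meet the criteria in follow-up: not in the documents; assumed 0.02 to 0.30.

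**Formulas**
- Literal rate under 5.4.3.2 = p·q + (1−p)·r
- First-time completers over the whole arm = (1−p)·r
- Recount share = p·q / [p·q + (1−p)·r]
- Recounts are the majority when r < p·q/(1−p)

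**Worked case, q = 0.9, r = 0.05**
- p = 25%: 0.225/(0.225 + 0.0375) = 86%
- p = 5%: 0.045/(0.045 + 0.0475) = 49%

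**Range of the recount share**
- p = 25%: from 0.125/(0.125 + 0.225) = 36% (q = 0.5, r = 0.30) to 0.25/(0.25 + 0.015) = 94% (q = 1, r = 0.02)
- p = 5%: from 0.025/(0.025 + 0.285) = 8% to 0.05/(0.05 + 0.019) = 72% at the same two corners

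**Break-even at q = 0.9**
- p = 25%: r = 0.225/0.75 = 30%
- p = 5%: r = 0.045/0.95 = 4.7%

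**Literal count against first-time count, q = 0.9**

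| Arm | r | Literal | First-time only, whole arm |
|---|---|---|---|
| p = 25%, N = 90 | 5% | 23.6 (26.3%) | 3.4 (3.8%) |
| p = 25%, N = 90 | 20% | 33.8 (37.5%) | 13.5 (15.0%) |
| p = 5%, N = 45 | 5% | 4.2 (9.2%) | 2.1 (4.8%) |
| p = 5%, N = 45 | 20% | 10.6 (23.5%) | 8.6 (19.0%) |

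**No late completion in either arm (r = 0)**
- q = 0.9: 0.25 × 90 × 0.9 ≈ 20, and 0.05 × 45 × 0.9 ≈ 2, so 20/90 (22%) against 2/45 (4%). Pooled rate 22/135 = 0.163; SE = √[0.163 × 0.837 × (1/90 + 1/45)] = 0.067; z = 0.178/0.067 ≈ 2.6; one-sided p about 0.004.
- q = 0.5: 11/90 against 1/45; by the same formula z ≈ 1.9, one-sided p about 0.03.

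These tests are unstratified with small control counts, so they only illustrate. They show that the literal measure can separate the arms with nobody completing NA in follow-up.

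**The case against.** The best defence is that SAP 5.4.3.2 matches the endpoint as named. The objectives tables (Protocol 3, SAP 1.1) also refer to participants meeting the criteria during follow-up without a restriction. Inclusion of Week 48 completers follows from silence, and the protocol's schedule has completion or re-treatment criteria assessed as applicable, which suggests completion is judged in those still on NA. This stands as a description of the text. It is also why the rule should be written out, since two programmers could produce very different tables.

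The second defence is that other outputs show late qualifiers. SAP 5.4.3.3 gives Kaplan-Meier curves for time to meeting the criteria. SAP 5.4.8 tabulates those who never met them at Weeks 48, 60, 72 and 96. SAP 4.1 counts participants in the extended follow-up phase, which is reserved for those who completed NA during follow-up. This partly stands, but the information is indirect. In 5.4.3.3 the clock starts at first intake, and meeting the criteria counts whether or not treatment stopped, so late events must be read from the tail of the curve. In 5.4.8 they appear as a fall between time points, and 4.1 is disposition. None of these corrects the named endpoint.

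Third, a reader might infer that the endpoint largely re-counts primary responders. The documents do not support that. They give neither q nor r. The JNJ-3989 decline is an average after three injections and covers HBsAg only. Protocol 4.2 notes that ALT and HBV DNA often rise after NA is stopped, and Arms 5 and 6 receive no JNJ-3989. In control, recounts are the majority only if late completion is below about 5%.

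Finally, the comparison carries no multiplicity adjustment, and no primary, key secondary, alpha or power figure is affected. That stands and limits the weight of the point.

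**Conclusion.** The point holds as a defect of definition. As written, 5.4.3.2 does not separate continued fulfilment of the criteria in Week 48 completers from first-time fulfilment in participants still on NA, whereas Protocol 6.6 raises follow-up completion only for the second group.

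The size is open. With q from 0.5 to 1.0 and r from 0.02 to 0.30, both assumed, recounts are 36–94% of the count at a 25% Week 48 rate and 8–72% in control. The firm part is the direction: for given q and r, an arm with a higher Week 48 rate has the larger recount share, so the mixing can favour JNJ-3989 arms in the CMH comparison even with no late completion. It is not shown that recounts dominate in every arm, or that the results would in fact be misread.

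**What to change.** In SAP 5.4.3.2, define the event as first meeting all four criteria in the follow-up phase while still on continued NA, among participants who did not complete NA at or before Week 48. Use tests up to the cut-off in Protocol 6.6: Follow-up Week 42, or Follow-up Week 36 for Arm 6.

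For the between-arm comparison, use all mITT participants in the arm as the denominator. Show Week 48 completers as a separate category beside the late completers. Give the rate among Week 48 non-completers descriptively only. That subset is defined after randomisation by an outcome that treatment affects (about 68 of 90 at a 25% rate against about 43 of 45 at 5%), so a test within it would lose the randomised comparison.

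The cost is SAP wording and a derived flag. Week 48 status is already derived under SAP 5.2.1, and SAP 5.4.1.2 refers to the CRF page for NA treatment disposition. The reported rate becomes smaller, as the table above shows. An arm with many Week 48 completers also has fewer participants left to complete late: at r = 20%, 15.0% against 19.0% in control. The two categories must therefore be read together.

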5.4.3.3. Time to NA Treatment Completion

Time to meet NA completion criteria is defined as the number of days between the date of first study intervention intake and the date of meeting NA completion criteria regardless of whether the participant actually discontinued treatment (i.e. the date of meeting NA completion criteria – the date of first study intervention intake + 1). The participants who withdrew early from the study before meeting NA completion criteria or who did not meet NA completion criteria will be censored at the last available lab assessment with non-missing ALT, HBV DNA, HBeAg and HBsAg results.

Time to meet NA completion criteria will be summarized by intervention arm. The Kaplan-Meier method will be used to estimate and plot the cumulative incidence by each intervention arm. The log-rank test will be performed to compare among the intervention arms. The median time with 90% CI will be estimated using Kaplan-Meier method. In addition, the hazard ratio and the corresponding 90% confidence interval will be estimated based on a stratified Cox's regression model by the 2 randomization stratification factors

5.4.4. NA Re-Treatment During Follow-Up

The number and proportion of participants who meet the criteria for NA re-treatment at any time during FU will be summarized descriptively by intervention arm. Only the subset of participants who meet the NA treatment completion criteria at any time during the study and actually stop NA treatment will be included in the analysis.

The proportion of participants who actually re-started NA treatment during the follow-up phase on the basis of the 'Study Drug Administration for ETV, TDF or TAF' CRF page will be summarized separately over time (e.g. FU Week12, 24, 48, etc.) by intervention arm.

Due to the Protocol Amendment #4 to update the criteria for NA re-treatment for participants who discontinued NA treatment at Week 48, the participants who met NA re-treatment criteria in follow-up will also be listed along with their respective criterion. The proportion of participants who met the criteria according to the flag on the CRF page of 'NA Re-treatment Criteria Assessment' during the follow-up phase was summarized over time by intervention arm prior to Protocol Amendment 4 approval.

A cross-tabulation of participants who actually re-started NA treatment (re-started/not restarted) versus participants who met the above criteria (met/not met) will be presented over time.

5.4.5. HBsAg, HBeAg, and HBV DNA

5.4.5.1. Values and Changes Over Time

HBsAg and HBeAg will be summarized by treatment history (not currently treated and virologically suppressed) and overall, and HBV DNA will only be summarized by treatment history.

Descriptive statistics on actual values (original unit and log10 transformed values) and changes from baseline (log10 transformed values) over time in HBsAg, HBeAg and HBV DNA will be summarized by intervention arm. Mean (+/- SE) plots of the actual values and the change from baseline (log10 transformed) will be presented over time per blood marker by intervention arm.

In addition, the change from baseline value to nadir (i.e. maximum decrease for each participant) in each blood marker will be summarized descriptively by intervention arm. Box plots of the changes to nadir in HBsAg, HBeAg, and HBV DNA will display the distribution by intervention arm.

Change from baseline based on log10 transform for quantitative HBsAg, HBeAg and HBV DNA will be analyzed using mixed effects model for repeated measures [MMRM]) including intervention arm, analysis time point (week), and 2 randomization stratification factors (HBeAg status at screening [positive versus negative] and treatment history [not currently treated versus virologically suppressed]) and baseline blood marker categorical variable as fixed effects. In addition, the above model will be augmented with an intervention arm-by-analysis week interaction term (i.e. treatment-by-time interaction term) to evaluate the change of treatment effect over time and the intervention arm-by-baseline interaction term. The covariance structure will include a random intercept at the level of the participant to capture between-participant variability, while within-participant variability will be captured with an unstructured (type=UN) covariance matrix. In case of convergence problems, simpler variance-covariance structures such as Toeplitz or AR (1) will be considered. The selection of any of these structures will be determined after exploration of the observed correlation structure. The LS mean of change from baseline, standard error (SE), 90% confidence interval (CI) and p-values will be provided.

Descriptive statistics on actual values (original unit and log10 transformed values) and changes from baseline (log10 transformed values) at end of treatment in HBsAg, HBeAg and HBV DNA, respectively, will be summarized by study intervention arm by outcome response (i.e. by NA

treatment completion criteria status at Week 48, by functional cure status at Week 72, and by partial cure status at Week 72, and for participants who achieved functional cure 24 weeks after stopping all study interventions regardless of meeting the NA completion criteria).

Cross-tabulations overtime and overall of quantitative versus qualitative HBsAg and HBeAg values, respectively, will also be presented.

Spaghetti plots for both absolute values and changes from baseline of HBsAg, HBeAg, and HBV DNA will be presented over time per blood marker by intervention arm and by selected subgroups (e.g. HBeAg status at baseline, HBV Genotype) and by outcome response (i.e. by NA treatment completion criteria status at Week 48, by functional cure status at Week 72, and by partial cure status at Week 72).

Waterfall plots for changes from baseline of HBsAg, HBeAg, and HBV DNA will also be presented.

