NA treatment completion criteria (described in Section 6.6) are included to explore the possibility of finite treatment. The treatment completion criteria which take ALT, HBV DNA, HBeAg and HBsAg levels into consideration, have been selected to ensure that only subjects with a chance of sustained off-treatment response are allowed to complete all study intervention. Across a range of studies, HBsAg levels below 100 IU/mL are consistently associated with favorable off-treatment response. ^{19,26} The stringent HBsAg cutoff of 10 IU/mL for NA treatment completion was chosen to account for the direct effect of JNJ-3989 on HBsAg levels.

Follow-up Procedures and Criteria for Re-initiation of NA Treatment

To ensure safety of patients during the follow-up phase, an ALT flare management plan is in place, including a high visit frequency for patients after completion of NA treatment (at Week 48 or later), and weekly visits for patients with $ALT/AST \ge 3x$ upper limit of normal (ULN) and $\ge 3x$ nadir until stabilization.

Increases in ALT and HBV DNA are frequently seen in patients after discontinuation of NA treatment. These ALT elevations can be reflecting an activation of the host cellular immune response and can as such lead to functional cure. Cases of fulminant HBV reactivation with fatal outcome were described after cessation of NA treatment, but the vast majority of such cases were described in patients with decompensated liver disease at the time of NA discontinuation. These patients are not eligible to participate in the study. Still, a vigilant follow-up of patients during this phase of the study is critical to ensure patient safety. Increases in ALT that are accompanied

by signs of decreased liver function, or an HBV DNA value of >100,000 IU/mL (irrespective of confirmation and/or ALT increase), will trigger immediate re-initiation of NA treatment based on protocol-defined NA re-treatment criteria (see Section 6.7).

Re-initiation of NA treatment is also required in case of confirmed HBeAg seroreversion (HBeAg positive after it was negative at NA completion), in case of confirmed* ALT increase (>5x ULN) in combination with increased HBV DNA replication (>2,000 IU/mL), and in case of confirmed* increased HBV DNA replication at higher levels (>20,000 IU/mL).

* At least 4 weeks apart

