5.1. Inclusion Criteria

Each potential participant must satisfy all of the following criteria to be enrolled in the study:

- 1. Adult male or female participants 18 (or the legal age of consent in the jurisdiction in which the study is taking place) to 65 years of age, inclusive.
- 2. Participants must be medically stable, with the exception of HBV disease, on the basis of physical examination, medical history, vital signs, and 12-lead ECG performed at screening. If there are abnormalities, they must be consistent with the underlying illness in the study population. This determination must be recorded in the participant's source documents and initialed by the investigator.
- 3. Participants must have chronic HBV infection documented by serum HBsAg positivity at screening. In addition, chronicity must be documented by serum HBsAg positivity at least 6 months prior to screening or alternative markers of chronicity (HBeAg positivity or HBV DNA positivity at least 6 months prior to screening, ALT elevation above ULN at least 6 months prior to screening without another cause than HBV infection, liver

biopsy, or documented transmission event at least 6 months prior to screening).

Note: if documentation of chronicity (as mentioned above) at least 6 months prior to screening is not available, participants may be included if HBsAg positive and negative for immunoglobulin M (IgM) antibodies to HBc antigen at screening.

- 4. Participants who are **not currently treated** (defined as not having been on HBV treatment, including NAs and IFN products within 6 months prior to screening), including **treatment-naïve** participants (defined as never having received HBV treatment, including NAs and IFN products) should have:
 - a. Serum HBV DNA at screening ≥2,000 IU/mL for HBeAg-negative participants and ≥20,000 IU/mL for HBeAg-positive participants, AND
 - b. ALT levels at screening <10x ULN AND >ULN on two measurements at least 3 months apart (one of which is at screening).
- 5. Virologically suppressed participants should:
 - a. be on stable HBV treatment, defined as currently receiving NA treatment (ETV, TDF, or TAF) for at least 6 months prior to screening and having been on the same NA treatment regimen (at the same dose) as used in this study (see Section 6.1) for at least 3 months at the time of screening, AND
 - b. have serum HBV DNA <60 IU/mL on two measurements at least 6 months apart (one of which is at screening), AND

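### The HBV DNA MMRM in SAP 5.4.5.1 averages suppressed and untreated participants into a difference that describes neither, and states no last week

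*SAP*

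**What the plan says.** SAP 5.4.5.1 (Values and Changes Over Time) opens with a reporting rule: HBsAg and HBeAg are shown by treatment history and overall, but "HBV DNA will only be summarized by treatment history". SAP 5.4.5.4 repeats the split for HBV DNA thresholds.

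The section then gives one model for three markers: "Change from baseline based on log10 transform for quantitative HBsAg, HBeAg and HBV DNA will be analyzed using mixed effects model for repeated measures", "including intervention arm, analysis time point (week), and 2 randomization stratification factors" plus a categorical baseline value of the marker. Next, "the above model will be augmented with an intervention arm-by-analysis week interaction term" "and the intervention arm-by-baseline interaction term". LS means with SEs, 90% CIs and p-values are promised. SAP 5.1.1 places such analyses at one-sided 0.05 without multiplicity adjustment.

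The section names no last week and has no rule for values taken after NA is stopped or re-started. The matching objective in SAP 1.1 covers both treatment and follow-up. The introduction to SAP 5 applies the Section 2.1 time points, which include follow-up, and says efficacy data are analysed by phase where applicable.

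Two design facts matter. Virologically suppressed participants must "have serum HBV DNA <60 IU/mL on two measurements at least 6 months apart" (Protocol 5.1). If the completion criteria are met at Week 44, "treatment with NA will also be completed at Week 48" (Protocol 6.6), and the protocol expects that "Increases in ALT and HBV DNA are frequently seen in patients after discontinuation of NA treatment" (Protocol 4.2).

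**The concern.** Change in HBV DNA is a named secondary endpoint, and this model supplies its inference. The two treatment-history groups start several log10 apart and have very different room to change. A model that lets them differ only by a constant gives one arm difference averaged over both, and readers will take that number as the antiviral effect.

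The missing last week raises a second issue. From Week 48, who is off NA depends on response, so an arm with more responders has more participants in whom HBV DNA can rise. If follow-up visits are modelled, the arm contrast there mixes drug effect with the NA stopping rule and can point against the better regimen.

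**Working it through.** The documents give no effect size, SD or power for this model, so there is no figure to reproduce.

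**1. Does the text pool?** Treatment history is listed as a fixed effect. In a model fitted within one history group it would be constant and could not be estimated. Taken literally, the model is fitted to both groups together. No term lets the arm effect, or the course over weeks, differ by history.

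**2. Room to fall.** Inputs: entry limits from Protocol 5.1 (below 60 IU/mL if suppressed; at least 2,000 or 20,000 IU/mL if untreated, by HBeAg status). Values below LLOQ are set to 15 IU/mL (target detected) or 5 IU/mL (not detected) in SAP 5.1.2, Table 3.

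- Suppressed, largest possible fall: log10(60/5) = 1.08. Starting below LLOQ with target detected: log10(15/5) = 0.48. Starting with target not detected: 0.
- Untreated, smallest fall on reaching <LLOQ: log10(2,000/15) = 2.12, or log10(20,000/15) = 3.12.

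**3. Attenuation.** Pooled difference = w × d(untreated) + (1 − w) × d(suppressed). Protocol 4.1 aims for 40% untreated, so w = 0.40. Take d(suppressed) = 0, meaning an effect confined to untreated participants.

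- d(untreated) = 1.0 gives 0.40; d(untreated) = 0.5 gives 0.20.
- If LS means weight the two strata equally, w = 0.50, giving 0.50 and 0.25.

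**4. Power.** This was simulated at a single visit with arm and treatment history in the model: 90 versus 45 participants, hence 36 versus 18 untreated; one-sided 0.05; assumed SD 1.0 in untreated participants.

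| True effect in untreated | Assumed SD in suppressed | Pooled estimate | Pooled power | Untreated-only estimate | Untreated-only power |
|---|---|---|---|---|---|
| 0.5 | 0.3 | 0.20 | 0.51 | 0.51 | 0.54 |
| 0.5 | 1.0 | 0.21 | 0.30 | 0.50 | 0.53 |
| 1.0 | 0.3 | 0.41 | 0.95 | 1.01 | 0.96 |
| 1.0 | 1.0 | 0.40 | 0.69 | 1.00 | 0.96 |

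The estimate is attenuated in every row. Power falls materially only when the suppressed group is assumed to be as variable as the untreated group. The simulation has no baseline terms.

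**5. Follow-up, if included.** Shift against the more effective arm = (share off NA in that arm − share off NA in control) × (mean log10 off NA − mean log10 on NA).

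- Shares: 25% and 5%, the 20-point contrast over 5% in Protocol 9.2 and SAP 1.4.
- On NA: log10(5) = 0.70 to log10(15) = 1.18, taking everyone on NA to be at the imputed values.
- Off NA: 3 log10 IU/mL, range 2 to 4. This is an assumption; the documents give no mean.

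At 3 log10: 0.20 × (3 − 1.18) = 0.36 to 0.20 × (3 − 0.70) = 0.46. At 2 log10 the lower end is 0.20 × (2 − 1.18) = 0.16. At 4 log10 the upper end is 0.20 × (4 − 0.70) = 0.66.

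As a cross-check, a rise from 15 to an assumed 200, 2,000 or 20,000 IU/mL gives 0.22, 0.42 or 0.62 log10. In a simulated two-group test (90 versus 45; assumed SD 0.3 on NA and 1.0 for the rebound), the one-sided 0.05 test favoured control in 61%, 87% and 90% of runs.

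**The case against.** **The opening rule may govern the model too.** On that reading HBV DNA is modelled within each history group, and the listed factor is left over from text shared by three markers. This is possible, but the section does not say so, and a programmer following the model statement would pool.

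**The arm-by-baseline term may separate the groups.** A cut between 60 and 2,000 IU/mL would make that term nearly an arm-by-history term, and stratum effects could be recovered. However, the HBV DNA baseline categories are not defined. The subgroup split in SAP 2.4.1 (100,000 IU/mL) applies to untreated participants only, and the categories in SAP 4.2.2 are mostly cumulative. The overall LS mean would still average the strata.

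**Follow-up may not be in the model.** This stands: a reader might infer that the SAP runs the model into follow-up, but SAP 5.4.5.1 does not say so. SAP 1.1 and SAP 5 only suggest it, and analysis by phase would allow separate fits. Separate fits would not remove the problem from the follow-up fit itself.

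**Follow-up data do not dilute the weekly on-treatment contrasts.** This also stands for the augmented model, where the arm-by-week term gives each week its own contrast. Attenuation on treatment comes from pooling the strata.

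**Other displays limit misreading.** SAP 5.4.5.1 plans individual profiles by completion status, and SAP 5.4.2 analyses HBV DNA <LLOQ off treatment without NA restart. The MMRM is a secondary analysis without multiplicity adjustment. This bears on priority, but leaves the reported LS mean hard to interpret.

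**Conclusion.** The point holds as a specification fault in a secondary analysis. As written, the model contradicts the section's own reporting rule and gives an arm difference that applies to neither group: about 0.4 of an effect confined to untreated participants, or 0.5 with equal stratum weights. This rests on the planned 40% share and on no effect in suppressed participants.

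Three stronger readings are not supported.

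- A material loss of power is not established. In one plausible case it is 0.51 against 0.54, and the larger losses depend on assumed SDs.
- A follow-up reversal of 0.82 to 1.04 log10 would need 50% versus 5% off NA. The 50% is the highest Arm 1 rate in Protocol Table 7, used there for comparing regimens. The planning contrast against control is 25% versus 5%, which gives 0.36 to 0.46 (0.16 to 0.66 over the assumed range). The reversal is conditional on follow-up being modelled and on an assumed level off NA.
- It does not follow that follow-up comparisons must be dropped. The objective includes follow-up, and a contrast regardless of NA status can be defended for a finite-treatment strategy if it is labelled as such.

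**What to change.** In SAP 5.4.5.1:

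- Fit the HBV DNA MMRM separately by treatment history and drop that factor. Alternatively, keep one model, add arm-by-history and arm-by-history-by-week terms, and report LS means by stratum.
- Name the not-currently-treated group, through Week 48, as the main on-treatment comparison.
- Define the HBV DNA baseline categories and state the last week of the model.
- For follow-up, show HBV DNA by arm and NA status (continued, stopped, re-started), and label any arm contrast as regardless of NA status.

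The cost is SAP wording and reprogramming, with no new data. The models are smaller (36 versus 18 untreated for a 90 versus 45 comparison), and there is no longer a single pooled HBV DNA p-value.
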